7.1 Eligible and Evaluable Subjects

- All subjects who receive ^{68}Ga -OPS202 are “eligible” subjects and will be included in the safety analysis.
- All eligible subjects with one or more readable ^{68}Ga -OPS202 PET and a readable ceCT scan will be included in the first component of the co-primary endpoint analysis to determine sstr2 positive prevalence.
- The following describes those subjects that are eligible and “evaluable” for the second component of the co-primary endpoint to assess the optimum timing of the PET scan following infusion of ^{68}Ga OPS202:
 - A readable ceCT scan
 - At least two ^{68}Ga -OPS202 PET scans that are readable (three images are to be acquired but 2 of these, MUST be readable by the central readers; if only two PET scans are acquired BOTH must be readable) with at least one avid lesion identified by central readers.

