11 STATISTICS

11.1 Analyses Populations

The following population will be used during statistical analyses:

- **Eligibility screened population:** All subjects screened (i.e. who signed the informed consent).
- **Safety population:** All subjects who received the dose of study IIP.
- **⁶⁸Ga-OPS202 screened population:** All subjects who received the dose of study IIP and for whom PET/CT scan images are readable for at least one timepoint. This population encompasses both subjects with sstr2 positive lesion(s) and those with sstr2 negative lesions (no avid lesion with ⁶⁸Ga-OPS202).
- **Sstr2 positive population:** All subjects who received the dose of study IIP and for whom ⁶⁸Ga-OPS202 PET/CT scan images are readable for at least one timepoint and have one avid lesion identified by central readers, ¹⁸F-FDG-PET/CT scan and a ceCT scan confirmed by the central readers.
- **Sstr2 positive evaluable population:** ⁶⁸Ga-OPS202 sstr2 positive population with at least two evaluable ⁶⁸Ga-OPS202 timepoints, ¹⁸F-FDG-PET/CT scan and a ceCT scan confirmed by the central readers.

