11.1.1 Populations Analysed

The co-primary analysis based on the primary efficacy endpoint to determine sstr2 positive percentage will use the ⁶⁸Ga-OPS202 screened population as the denominator. The co-primary analysis based on the primary efficacy endpoint to assess optimum imaging timing of the PET scan following ⁶⁸Ga-OPS202 injection will be performed on the sstr2 positive evaluable population. In addition, secondary/confirmatory analysis may be performed on the sstr2 positive population.

The analyses of safety data will be performed based on the safety population.

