2 SUBJECT POPULATIONS (ANALYSIS SETS)

[figure not shown]
The following populations will be used during statistical analyses:

- **Eligibility screened population:** All subjects screened (i.e. who signed the informed consent).
- **Safety population:** All subjects who received the dose of study IIP.

- **^{68}Ga -OPS202 screened population:** All subjects who received the dose of study IIP and for whom PET/CT scan images are readable for at least one timepoint. This population encompasses both subjects with sstr2 positive lesion(s) and those with sstr2 negative lesions (no avid lesion with ^{68}Ga -OPS202).
- **Sstr2 positive population:** All subjects who received the dose of study IIP and for whom ^{68}Ga -OPS202 PET/CT scan images are readable for at least one timepoint and have one avid lesion identified by central readers, ^{18}F -FDG-PET/CT scan and a ceCT scan confirmed by the central readers.
- **Sstr2 positive evaluable population:** ^{68}Ga -OPS202 sstr2 positive population with at least two evaluable ^{68}Ga -OPS202 timepoints, ^{18}F -FDG-PET/CT scan and a ceCT scan confirmed by the central readers. A ^{68}Ga -OPS202 timepoint is considered evaluable if it shows at least one avid lesion.

Study populations are summarized in the figure below.

Figure 4 Study populations

For each population of analysis, further description and specificities are provided below.

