2.1 Efficacy populations

2.1.1 *⁶⁸Ga-OPS202 screened population*

The ⁶⁸Ga-OPS202 screened population includes all subjects who received the dose of study IIP with one or more readable ⁶⁸Ga-OPS202 PET and a readable ceCT scan.

The assessment of ⁶⁸Ga-OPS202 PET scan and ceCT scan readability will be based on the imaging read named “Confirmation read”, provided by ICL.

This population encompasses both subjects with sstr2 positive lesion(s) and those with sstr2 negative lesions (i.e. no avid lesion with ⁶⁸Ga-OPS202).

2.1.2 *Sstr2 positive population*

The sstr2 positive population includes all subjects who received the dose of study IIP and for whom ⁶⁸Ga-OPS202 PET/CT scan images are readable for at least one timepoint and have one avid lesion identified by central readers.

The assessment of ⁶⁸Ga-OPS202 PET scan readability and the presence of avid lesions will be based on the imaging read named “Confirmation read”, provided by ICL.

Subjects are also required to have a ¹⁸F-FDG-PET/CT scan and a readable ceCT scan.

2.1.3 *Sstr2 positive evaluable population*

The sstr2 positive evaluable population includes all subjects from the ⁶⁸Ga-OPS202 sstr2 positive population with at least two evaluable timepoints. Subject are also required to have a ¹⁸F-FDG-PET/CT scan and a readable ceCT scan.

Evaluable subjects are those with a ceCT scan, ¹⁸F-FDG-PET scan and at least two ⁶⁸Ga-OPS202 PET scans that are readable (three images are to be acquired but two of these must be readable by the central readers. If only two PET scans are acquired both must be readable) with at least one avid lesion identified on at least 2 timepoints by central readers.

The assessment of ⁶⁸Ga-OPS202 PET scan readability and the presence of avid lesions will be based on the blinded imaging read “⁶⁸Ga-OPS202 PET Independent Review” (two readers and potential adjudication), provided by ICL.

Listings of subjects regarding inclusion in each population and satisfying the population definition and associated data will be reviewed by the study team.

The reasons for subject exclusion from each of the populations will be listed and tabulated.

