2.3 Primary population

The co-primary analysis based on the primary efficacy endpoint to determine sstr2 positive percentage will use the ^{68}Ga -OPS202 screened population as the denominator. The co-primary analysis based on the primary efficacy endpoint to assess optimum imaging timing of the PET scan following ^{68}Ga -OPS202 injection will be performed on the sstr2 positive evaluable population.

In addition, as a supportive post-hoc analysis, the sstr2 positive prevalence may also be evaluated on the agreed optimum timepoint population.

All secondary and exploratory efficacy endpoints will be evaluated on the sstr2 positive evaluable population.

The assessment of safety and tolerability will be based on the safety population.

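### The SAP drops subjects avid at one timepoint only from the comparison of timepoints, and does not declare the rule

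*SAP*

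**What the plan says.** **SAP.** Section 2 builds the sstr2 positive evaluable population on evaluable timepoints and states that a "timepoint is considered evaluable if it shows at least one avid lesion". Section 2.1.3 repeats the condition for the subject: two readable scans "with at least one avid lesion identified on at least 2 timepoints by central readers". It adds that "PET scan readability and the presence of avid lesions will be based on the blinded imaging read", meaning the Independent Review by two readers with possible adjudication. Sections 2.3 and 3.2.1.1 use this population for the second co-primary component. For the rest, Section 2.3 says "All secondary and exploratory efficacy endpoints will be evaluated on the sstr2 positive evaluable population", and Section 3.2.1.2 confirms that only this set is used.

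**Protocol.** Section 11.1 describes the same population as the "sstr2 positive population with at least two evaluable" timepoints, without defining the adjective. Section 7.1, written for the timing component, asks for two readable scans ("if only two PET scans are acquired BOTH must be readable) with at least one avid lesion identified by central readers") and gives no number of timepoints for the avid lesion. Section 3.2.1 defines avidity at one of the acquisition times. The Figure 1 footnote, which the SAP reproduces, mentions readability only.

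**Wider set.** Protocol 11.1.1 left an option open: "In addition, secondary/confirmatory analysis may be performed on the sstr2 positive population". SAP 2.3 does not carry it over. Its only supportive analysis concerns prevalence: "as a supportive post-hoc analysis, the sstr2 positive prevalence may also be evaluated on the agreed optimum timepoint population". SAP Section 5 declares the removal of analyses after early termination and does not mention the population definition.

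**The concern.** The timing component asks whether the lesions detected differ between acquisition times. A subject with two or three readable scans and avid lesions at one time only differs between times in the plainest way, and the SAP rule removes her. Inclusion then depends on a variable closely related to the lesion count being compared.

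The two variables are not identical. Avidity counts in any organ, so a subject with a node avid at two times stays in whatever her breast lesion shows. Nor does avidity at one time prove a real timing effect, because the definition includes a 1.5-fold uptake threshold that a lesion may cross by a small margin.

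At stake is the evidence for choosing the optimal time. If such subjects exist, their counts, quality scores and SUVs are assigned to no output in the SAP text, and the choice can be distorted in either direction.

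**Working it through.** No figure in the plan depends on this rule alone, so the check is a comparison of the two rules. The readability rule means two readable scans and an avid lesion at any time. The SAP rule means an avid lesion at two or more times. A detected lesion is taken as an avid lesion, as in SAP 3.1.2 (c).

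**1. Subject patterns, three readable scans.** There are 2³ − 1 = 7 patterns with avidity at some time. The readability rule admits 7. The SAP rule admits 4 and drops 3 (0.5 h only, 1 h only, 2 h only).

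**2. Breast lesion together with other lesions.** Let b be the pattern of one breast lesion and o the pattern of all other lesions. A subject is removed if b OR o is positive at fewer than two times. A discordant b (seen at some times but not all) is removed only if b is positive once and o is empty or positive at that same time.

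| Readable scans | Discordant b | Patterns of o | Combinations | Removed |
|---|---|---|---|---|
| 3 | 6 | 8 | 48 | 3 × 2 = 6 |
| 2 | 2 | 4 | 8 | 2 × 2 = 4 |

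With no other avid lesion, the rule removes 3 of 6 discordant breast patterns (three scans) or 2 of 2 (two scans). With other lesions avid at two or more times it removes none. With exactly two readable scans, every admitted subject is avid at both, so any-lesion detection is equal by construction; counts and quality scores can still differ. These are counts of logical patterns, not probabilities.

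**3. Data lost per dropped subject with three readable scans** (listings in SAP 3.2.1.1). Breast counts: 3 timepoints × 3 results (two readers and final) = 9. Breast quality scores: 3 timepoints × 2 readers = 6.

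**4. Effect on the comparison.** The documents give no pattern data, so the inputs here are assumed: one breast lesion per subject and no other lesion. If aᵢ is the number of subjects avid at time i only, the SAP rule changes the difference between times i and j by aᵢ − aⱼ lesions.

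- Difference hidden: 16 subjects, k avid at 1 h only, the rest at all times. Totals at 0.5/1/2 h for k = 1 are 15/16/15, becoming 15/15/15. For k = 3, 13/16/13 becomes 13/13/13.
- Difference enlarged: 5 subjects avid at all times, 3 at 0.5 h and 2 h, 2 at 1 h only. Totals 8/7/8 become 8/5/8, so the gap against 1 h grows from 1 lesion to 3.
- Share of subjects lost for k = 1: 1/16 = 6.25%, 1/10 = 10%, 1/5 = 20%.

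**5. Completion and futility counts.** Both use the evaluable population. The plan expects 16 evaluable of 54, or 29.6%. It states no prevalence, so 54 cannot be reproduced from its own inputs; 16/0.30 = 53.3, rounded up to 54, needs an assumed 30%. Suppose that 16/54 is the rate of avidity at any time and that a share f of those subjects is avid once only. The evaluable rate is then q = (16/54)(1 − f). The chance of stopping is P(X₃₀ < 3) + P(X₃₀ ≥ 3 and X₅₀ < 8), exact binomial, on the first 30 and first 50 subjects.

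| f (assumed) | Expected evaluable of 54 | Enrolment for 16 | Chance of meeting a futility rule |
|---|---|---|---|
| 0 | 16.0 | 54 | 1.0% |
| 0.1 | 14.4 | 60 | 2.8% |
| 0.2 | 12.8 | 68 | 7.3% |
| 0.3 | 11.2 | 78 | 16.5% |

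**The case against.** The strongest reply is that the SAP chose a permissible reading. In Protocol 7.1 the avid lesion can be attached grammatically to the scans, and Protocol 11.1 says readable for one population and evaluable for the next, which suggests different meanings. Defining an open term is a SAP's job, and the rule is stated twice. This stands to the extent that the SAP does not contradict the protocol. But the definition of avidity at one time, the Figure 1 footnote and the absence of a timepoint count in Protocol 1.6 and 7.1 all favour the wider reading. A choice that decides who enters a co-primary analysis belongs in Section 5.

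Second, SAP 2.1.3 might mean a lesion that qualifies as avid once and is visible twice, which would drop fewer subjects. A subject whose lesions are seen at one time only is dropped under either reading.

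Third, the wider analysis in Protocol 11.1.1 was optional, and the listing templates in SAP Appendix 2 are not available here. An extra listing there cannot be ruled out, but the SAP text confines these analyses to the evaluable set.

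Fourth, the impact is limited. No tests are planned, efficacy is only listed after early termination, and reasons for exclusion are listed and tabulated. Dropped subjects also stay in the prevalence numerator if the separate Confirmation read finds an avid lesion. All of this stands and lowers the priority. However, once listings are the only evidence on timing, a subject left out of them is left out of that evidence.

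**Conclusion.** The concern holds. The SAP selects the timing population on a variable tied to the timing endpoint, does not declare the choice as a reading of an undefined protocol term, and assigns no timing output to the wider population.

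The exact size is 3 of 7 avidity patterns dropped with three readable scans, and 9 breast counts and 6 breast quality scores lost per such subject. The size in this trial is unknown, because the documents give no rate of avidity at one time only; it is nil if no such subject exists. The distortion has no fixed direction. The totals in step 4 and the stopping probabilities in step 5 are illustrations under assumed inputs. The point should be fixed, but it does not threaten a confirmatory conclusion, because the plan draws none.

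**What to change.** 1. SAP 2: define a timepoint as evaluable when the central readers can read its ⁶⁸Ga-OPS202 scan, and say how reader disagreement on readability is settled.
2. SAP 2.1.3: require an avid lesion at any timepoint, still judged on the Independent Review. Keep the requirements for two readable scans, the ceCT and the ¹⁸F-FDG-PET/CT.
3. SAP 3.2.1.1 and 3.2.1.2: list a readable scan without an avid lesion as a count of 0 and an unreadable scan as missing. This extends the conventions the SAP already has for relative lesion counts and quality scores.
4. SAP 5: state that Protocol 11.1 left the term undefined, that it is read as readable in line with Protocol 7.1, and which definition fed the 16-subject completion and futility counts. Since the study has ended, nothing further is needed on those counts.
5. If the two-timepoint set is kept, use it only for a labelled supportive listing and declare it in Section 5.

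The cost is SAP wording, one population flag and rerun listings. Two readers read all images and the present rule is itself judged on the Independent Review, so the count reads should exist. The quality comparison is the last step of the read, and the Imaging Review Charter is not available here. Confirm with the imaging core laboratory that subjects avid at one time only received the count, quality and SUV reads, and list as missing any not done.

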2.1 Efficacy populations

2.1.1 *⁶⁸Ga-OPS202 screened population*

The ⁶⁸Ga-OPS202 screened population includes all subjects who received the dose of study IIP with one or more readable ⁶⁸Ga-OPS202 PET and a readable ceCT scan.

The assessment of ⁶⁸Ga-OPS202 PET scan and ceCT scan readability will be based on the imaging read named “Confirmation read”, provided by ICL.

This population encompasses both subjects with sstr2 positive lesion(s) and those with sstr2 negative lesions (i.e. no avid lesion with ⁶⁸Ga-OPS202).

2.1.2 *Sstr2 positive population*

The sstr2 positive population includes all subjects who received the dose of study IIP and for whom ⁶⁸Ga-OPS202 PET/CT scan images are readable for at least one timepoint and have one avid lesion identified by central readers.

The assessment of ⁶⁸Ga-OPS202 PET scan readability and the presence of avid lesions will be based on the imaging read named “Confirmation read”, provided by ICL.

Subjects are also required to have a ¹⁸F-FDG-PET/CT scan and a readable ceCT scan.

2.1.3 *Sstr2 positive evaluable population*

The sstr2 positive evaluable population includes all subjects from the ⁶⁸Ga-OPS202 sstr2 positive population with at least two evaluable timepoints. Subject are also required to have a ¹⁸F-FDG-PET/CT scan and a readable ceCT scan.

Evaluable subjects are those with a ceCT scan, ¹⁸F-FDG-PET scan and at least two ⁶⁸Ga-OPS202 PET scans that are readable (three images are to be acquired but two of these must be readable by the central readers. If only two PET scans are acquired both must be readable) with at least one avid lesion identified on at least 2 timepoints by central readers.

The assessment of ⁶⁸Ga-OPS202 PET scan readability and the presence of avid lesions will be based on the blinded imaging read “⁶⁸Ga-OPS202 PET Independent Review” (two readers and potential adjudication), provided by ICL.

Listings of subjects regarding inclusion in each population and satisfying the population definition and associated data will be reviewed by the study team.

The reasons for subject exclusion from each of the populations will be listed and tabulated.

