- (6) The ^{68}Ga -OPS202 PET scans will be compared with the ^{18}F -FDG-PET scan (with ceCT).

(a) Primary Efficacy Endpoint and Evaluation

The co-primary endpoint is therefore calculated in the following way:

- (1) The number of subjects with newly diagnosed breast cancer with primary sstr2 positive lesions identified by ^{68}Ga -OPS202 at any timepoint, divided by the total number of subjects imaged to obtain the prevalence in this study population.
- (2) The identification of the optimum acquisition time(s) based on differences in the number of lesions identified at each scan, and the reader interpretation of the optimum image in the primary breast lesions. The optimum image acquisition time could be one, two or all three acquisitions timepoints i.e. no noticeable difference between 0.5, 1 and 2 hours post infusion.

(b) Secondary Efficacy Endpoints and Evaluations*Key Secondary Endpoint:*

- Differences in the number of lesions detected by ^{68}Ga -OPS202 between the three PET acquisition timepoints (0.5, 1 and 2 hours), and reader interpretation of optimal image(s) in nodular and metastatic lesions. Significant uptake of ^{68}Ga -OPS202 for the evaluation of a lesion is an avid lesion defined by the blinded readers at one of the acquisition timepoints as an easily identifiable lesion radiologically, where there has been clear focal uptake of ^{68}Ga -OPS202 and 1.5-fold or greater uptake than in the non-tumoural liver and lung parenchyma.
- The SUV_{mean} and SUV_{max} in the primary lesion between each of the three timepoints, measured in the most avid lesions (using the ^{68}Ga -OPS202 scans). This is assessed by the tumour-to-background ratio in the primary tumour and each of the major anatomic sites (liver, lymph nodes, bone, lungs and brain); the background consists of non-tumoural liver parenchyma or aortic blood where sufficient liver is not available. Identification of lesions to be used will be made by one of the two primary readers.

Other Secondary Endpoints:

- Comparison to standard-of-truth for the primary breast tumour:
 - $(^{68}\text{Ga}\text{-OPS202 PET/CT}) / (^{18}\text{F}\text{-FDG-PET/CT})$
 - For each acquisition time of ^{68}Ga -OPS202 PET.

This will be repeated for each of the other anatomical locations:

- Lymph nodes
- Liver
- Axial/appendicular skeleton
- Lungs
- Brain

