11.4.4 Efficacy Evaluation

As indicated in Section 7, the first component of the co-primary endpoint is the percentage of subjects with sufficiently avid lesion(s) to be identified as a sstr2 positive lesion. This will be a simple percentage calculation (number of subjects in sstr2 positive population / number of subjects in ⁶⁸Ga-OPS202 screened population). The second component of the co-primary efficacy variable is the differences in the number of lesions detected by ⁶⁸Ga-OPS202 between the three PET acquisition timepoints (0.5, 1 and 2 hours) in the primary breast lesions. The second component of the co-primary efficacy variable will be summarised by each of the three PET acquisition timepoints (0.5, 1 and 2 hours). The results could identify that one, two or all three timepoints have equal validity for future studies in this population.

As indicated in Section 7, the secondary efficacy variables are the variables measured at Visit 2 after the i.v. administration of the IIP, listed below:

Key Secondary Endpoint:

- Differences in the number of lesions detected by ⁶⁸Ga-OPS202 between the three PET acquisition timepoints (0.5, 1 and 2 hours) and reader interpretation of optimal image(s) in nodular and metastatic lesions. Significant uptake of ⁶⁸Ga-OPS202 for the evaluation of a lesion is an avid lesion defined by the blinded readers at one of the acquisition timepoints as an easily identifiable lesion radiologically, where there has been clear focal uptake of ⁶⁸Ga-OPS202 and 1.5-fold or greater uptake than in the non-tumoural liver and lung parenchyma.
- The SUV_{mean} and SUV_{max} in the primary lesion between each of the three timepoints, measured in the most avid lesions (using the ⁶⁸Ga-OPS202 scans). This is assessed by

the tumour-to-background ratio in the primary tumour and each of the major anatomic sites (liver, lymph nodes, bone, lungs and brain); the background consists of non-tumoural liver parenchyma or aortic blood where sufficient liver is not available. Identification of lesions to be used will be made by one of the two primary readers.

Other Secondary Endpoints:

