3.2.1.1 Primary efficacy analysis

First component of the co-primary endpoint

The first component of the co-primary endpoint is the percentage of subjects with sufficiently avid lesion(s) to be identified as a sstr2 positive lesion, i.e. the sstr2 positive prevalence in this study population. Avid is defined by the blinded readers at one of the timepoints as an easily identifiable lesion radiologically, where there has been clear focal uptake of ⁶⁸Ga-OPS202.

This will be a simple percentage calculation:

$$\begin{aligned} & \text{Percentage of subjects with avid lesion identified as sstr2 positive lesion} \\ &= \frac{\text{Number of subjects in sstr2 positive population}}{\text{Number of subjects in } ^{68}\text{Ga} - \text{OPS202 screened population}} \end{aligned}$$

A listing with the subjects in sstr2 positive population and the subjects in the ⁶⁸Ga-OPS202 screened population will be provided in order to allow computing this percentage.

Second component of the co-primary endpoint

The second component of the co-primary endpoint is based on both image quality and lesion count using the sstr2 positive evaluable population.

The selection of the optimal PET acquisition time will be done by choosing the timepoint with superior images based on overall image quality and observed higher number of lesions detected.

The number of lesions detected by ⁶⁸Ga-OPS202 in the primary breast lesions will be reported at each of the three PET acquisition timepoints (0.5, 1 and 2 hours).

Individual values of number of lesions detected by ⁶⁸Ga-OPS202 in the primary breast lesions (result from both readers as well as final result) will be listed by subject and by PET acquisition timepoint.

Image quality

After blinded reading, the readers will compare the three scans (the three acquisitions of ⁶⁸Ga-OPS202) contemporaneously for each subject and note which image(s), if any, provides superior images based on overall image quality and lesion count.

This qualitative assessment will be performed using a quality score.

For each PET/CT assessment, each independent blinded reader will perform a direct comparison of the three ⁶⁸Ga-OPS202 scans acquired at different times (0.5, 1 and 2 hours) in the primary breast lesions. The readers will be allowed to select whether one, two or all three acquisitions are optimal, attributing a score for each assessment. The readers will be blinded to timepoint sequence.

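### First co-primary percentage: an avid subject without an FDG-PET/CT scan stays in the denominator but drops out of the numerator, so the stated formula is too low by m/N (m = avid subjects without FDG)

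*SAP*

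**What the plan says.** **Formula.** Protocol 11.4.4 gives the first co-primary component as "number of subjects in sstr2 positive population / number of subjects in" the ⁶⁸Ga-OPS202 screened population. SAP 3.2.1.1 repeats it, and SAP 2.3 confirms the denominator.

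**Denominator.** SAP 2.1.1 takes subjects who "received the dose of study IIP with one or more readable" ⁶⁸Ga-OPS202 PET and a readable ceCT. The shorter form in Protocol 11.1 (repeated in SAP 2) is: "All subjects who received the dose of study IIP and for whom PET/CT scan images are readable for at least one timepoint". Neither form mentions FDG.

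**Numerator.** SAP 2.1.2 starts from avid subjects and then adds: "Subjects are also required to have a ¹⁸F-FDG-PET/CT scan and a readable ceCT scan". Protocol 11.1 and the summary in SAP 2 carry the same condition, in the words "FDG-PET/CT scan and a ceCT scan confirmed by the central readers".

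**Endpoint.** SAP 3.1.1(a) defines positivity by avidity on ⁶⁸Ga-OPS202. Protocol 7(a)(1) counts "The number of subjects with newly diagnosed breast cancer with primary sstr2 positive lesions identified by" ⁶⁸Ga-OPS202 at any timepoint, "divided by the total number of subjects imaged to obtain the prevalence in this study population". Protocol 7.1 admits to this component anyone dosed who has a readable ⁶⁸Ga-OPS202 PET and a readable ceCT. None of the three sets an FDG condition.

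**The concern.** FDG is the standard of truth for the relative lesion count. It plays no part in deciding whether a lesion is avid on ⁶⁸Ga-OPS202. Using a population that requires FDG as the numerator, over a population that does not, turns a missing comparison scan into a negative ⁶⁸Ga-OPS202 result. The screened population is described as sstr2 positive subjects plus those with no avid lesion. An avid woman without FDG belongs to the first group by that description, yet the formula counts her with the second.

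Nothing later in the plan puts this right. Missing efficacy data are not imputed (SAP 3.2.3.1). Recruiting an additional subject after a missed exam (Protocol 11.2) does not take the first subject out of the denominator.

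At stake is the prevalence figure, one of the study's two co-primary results.

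**Working it through.** **Inputs.**
- N: subjects in the ⁶⁸Ga-OPS202 screened population (SAP 2.1.1). The final N is not in the documents.
- A: those of the N with at least one avid lesion.
- m: those of the A without an FDG-PET/CT scan. The documents give no value.
- Planned figures (SAP 1.3.4): 54 enrolled to obtain around 16 sstr2 positive evaluable subjects, with no formal sample size calculation.

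**Step 1, the plan's own figure.** The plan states no prevalence. Its yield implies 16/54 = 29.6%.

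**Step 2, the identity.** Under SAP 2.1.1 and 2.1.2 a readable ceCT is required on both sides, so FDG is the only scan condition that differs.
- Stated formula: (A − m)/N
- All avid subjects: A/N
- Difference: (A − m)/N − A/N = −m/N

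A non-avid subject without FDG is in the denominator and not in the numerator either way, so she has no effect. The identity does not depend on what ended recruitment.

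**Step 3, at the planned size.** Take A = 16 and N = 54 as an illustration:

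| m | Stated formula | All avid | Difference (points) |
|---|---|---|---|
| 0 | 16/54 = 29.6% | 29.6% | 0 |
| 1 | 15/54 = 27.8% | 29.6% | −1.9 |
| 2 | 14/54 = 25.9% | 29.6% | −3.7 |
| 3 | 13/54 = 24.1% | 29.6% | −5.6 |

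**Step 4, smaller N.** SAP section 5 says the study was terminated early with limited data. The cost of one affected subject is:
- N = 10 (assumed): 1/10 = 10.0 points. For example, 3 of 10 avid is 30%, reported as 2/10 = 20%.
- N = 20 (assumed): 1/20 = 5.0 points.
- N = 30 (the first futility checkpoint, Protocol 3.7): 1/30 = 3.3 points.

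**Step 5, how likely.** Assume, since the documents do not say, that each avid subject independently lacks FDG with probability q. With A = 3 and N = 10, P(m ≥ 1) = 1 − (1 − q)³ and the expected bias is −3q/10:

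| q | P(m ≥ 1) | Expected bias (points) |
|---|---|---|
| 0% | 0% | 0 |
| 2% | 1 − 0.941192 = 5.9% | −0.6 |
| 5% | 1 − 0.857375 = 14.3% | −1.5 |
| 10% | 1 − 0.729 = 27.1% | −3.0 |

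**The case against.** **No case with m > 0 is shown.** FDG is part of routine work-up, may be done from screening onward, must be acquired (Protocol 3.6), and is arranged at Day 2 if still outstanding (Protocol 3.1). If the sponsor ends the study, subjects still in it complete their scheduled procedures (Protocol 3.7). This stands: m may well be zero. A subject may nevertheless withdraw at any time (SAP 1.3.2.4), including after the ⁶⁸Ga scans and before FDG, so the definitions do not guarantee zero.

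**The target is unsettled.** Protocol 7(a)(1) speaks of primary lesions and of all subjects imaged. Measured against that wording, the stated formula could also be too high, because it admits subjects whose only avid lesion is nodal or metastatic and drops subjects without a readable ceCT. This stands as a separate inconsistency. It does not change the effect of the FDG condition, which taken alone can only lower the figure. The size m/N refers to the SAP 2.1.1 and 2.1.2 definitions. Under the short forms in Protocol 11.1 and SAP 2, avid subjects without ceCT could be lost in the same way.

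**The small N values are invented and precision is poor.** True. At 3 of 10 the exact 95% interval runs from about 7% to 65%. An imprecise estimate is still better without a known one-sided error.

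**The planned outputs already show the problem.** SAP 3.2.1.1 promises that a listing of the two sets, the sstr2 positive and the ⁶⁸Ga-OPS202 "screened population will be provided in order to allow computing this percentage". Reasons for exclusion are tabulated too. A careful reader could therefore recompute by hand, but anyone applying the formula as written would get the low figure.

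**Changing a co-primary numerator after the termination decision is awkward.** The FDG condition and the formula are both in the approved protocol, and a footnote would disturb less. The timing is a real drawback and must be documented. The revised rule follows endpoint text that is already in the plan, and SAP section 5 already records departures from the protocol's analyses.

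**Conclusion.** The concern holds. Under SAP 2.1.1 and 2.1.2 the stated formula gives (A − m)/N where the endpoint definition calls for A/N, so it is too low by m/N. The FDG condition can only push the figure down, and it has no effect if every avid subject has an FDG scan.

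The defect is latent. The documents give neither m nor the final N, so the realised error may be nil. If m = 1, it is 1.9 points at the planned 54 and 3.3 at 30, rising to 10.0 at an assumed 10. The mismatch and the identity are certain from the text. The probabilities in the check rest on assumed missing rates. It should be fixed, because a co-primary formula should not give a wrong figure whenever one comparison scan is missing.

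**What to change.** 1. In SAP 3.2.1.1, define the numerator as subjects in the screened population of SAP 2.1.1 who have at least one avid lesion at any timepoint, on the read that SAP 2.1.2 names, whether or not an ¹⁸F-FDG-PET/CT scan was done.
2. Leave the sstr2 positive evaluable population (SAP 2.1.3) as it is. The second co-primary component and all secondary and exploratory endpoints use it.
3. Record the change and its reason in SAP section 5, stating that it replaces the formula of Protocol 11.4.4. Reconcile it there with Protocol 7(a)(1): counting any avid lesion follows SAP 3.1.1(a) rather than the restriction to primary lesions, and the screened-population denominator follows Protocol 7.1 and SAP 2.3 rather than all subjects imaged.
4. Report m. If it is zero, say that both formulas give the same percentage. If it is not, the reader can recover the protocol's figure by subtracting m/N.

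**Cost.** One numerator definition, one entry in SAP section 5 and one reported count. No new data, analysis set or protocol amendment is needed. The drawback is a change to a co-primary numerator after the decision to terminate, which the section 5 entry must state openly.
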